### 2.3 Study Endpoints

#### 2.3.1 Primary Endpoints

The following primary safety endpoints will be evaluated:

- AEs within 72 hours post-dosing.
- AEs leading to discontinuation or temporary suspension of infusion.
- AEs and SAEs in healthy adults up to 84 days post- administration of a single COVID-HIGIV dose.

The following primary PK endpoints (based on PK sample test results of an immunobinding IgG assay and a pseudovirus neutralization assay) will be evaluated in healthy adults:

- Primary PK Endpoints (at each of the three COVID-HIGIV dose levels):
  - $AUC_{0\text{-last}}$ : area under the concentration-time curve from time 0 to the last quantifiable concentration after dosing.
  - $AUC_{0\text{-inf}}$ :  $AUC_{0\text{-last}}$  plus the additional area extrapolated to infinity after dosing.
  - $AUC_{0\text{-14d}}$  after dosing.
  - $AUC_{0\text{-28d}}$  after dosing.
  - $C_{\max}$ : maximum observed concentration after dosing.
  - $T_{\max}$ : time at which  $C_{\max}$  occurs after dosing.
  - $C_{\min 28d}$ : observed or estimated concentration at 28 days after dosing.
  - $\lambda_z$ : terminal elimination rate constant after dosing.
  - $T_{1/2}$ : apparent terminal elimination half-life after dosing.

- CL: systemic clearance after dosing.
- $V_Z$ : volume of distribution after dosing.

**Secondary PK Endpoints:** following body weight normalized PK parameters will be estimated as PK parameter divided by subject body weight (kg) at baseline.

- CmaxBWN: Body weight normalized Cmax
- Cmin28dBWN: Body weight normalized Cmin28d
- $AUC_{0-14d}BWN$ : Body weight normalized  $AUC_{0-14d}$
- $AUC_{0-28d}BWN$ : Body weight normalized  $AUC_{0-28d}$
- $AUC_{0-last}BWN$ : Body weight normalized  $AUC_{0-last}$
- $AUC_{0-inf}BWN$ : Body weight normalized  $AUC_{0-inf}$

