**Table 1**

Study Arm	No. of Subjects	Treatment*	Study Arm Label
1	8	COVID-HIGIV Dosage 1	COVID-HIGIV 100 mg/kg
2	8	COVID-HIGIV Dosage 2	COVID-HIGIV 200 mg/kg
3	8	COVID-HIGIV Dosage 3	COVID-HIGIV 400 mg/kg
4	4	Placebo (saline)	Placebo

\* Note: COVID-HIGIV Dosage 1-3 are prepared by IP volume (mL) based on subject body weight (kg).

COVID-HIGIV protein concentration  $\approx$  100 mg/mL, the dosages in study arm label are in the unit of mg/kg.

Dosage 1: prepared by COVID-HIGIV volume ( $\approx$ 1 mL/kg), with a maximum of 100 mL, labeled as 100 mg/kg,

Dosage 2: prepared by COVID-HIGIV volume ( $\approx$ 2 mL/kg), with a maximum of 200 mL, labeled as 200 mg/kg.

Dosage 3: prepared by COVID-HIGIV volume ( $\approx$ 4 mL/kg), with a maximum of 400 mL, labeled as 400 mg/kg.

[COVID-HIGIV]  
[EBS-CVH-003]

Eligible subjects will be randomized 2:2:2:1 to four study treatment arms to receive a single IV infusion of COVID-HIGIV at one of three dose levels or saline placebo.

The enrollment/dosing of the first seven subjects in the study will be staggered wherein no more than three subjects will be dosed on the same day (to be dosed at least one hour apart). Principal Investigator (PI) and the Sponsor's Medical Monitor (MM) will review blinded data (up to 24 hours after end of IV infusion) before proceeding with dosing subsequent set of remaining subjects for the stagger. Available safety (blinded) data will be reviewed by Study Monitoring Committee (SMC) (consisting of at least three independent external members) after seven subjects from Cohort A have completed at least 72 hours of safety follow-up. If unblinding of the safety data is required, closed session by the SMC will be held. An overall decision by the SMC will be made whether to proceed with full randomization and dosing of the remaining study subjects.

Following dosing, each subject will stay overnight in the inpatient unit for close observation; each dosed subject will be discharged from the inpatient unit once all assessments at 24 hours post-dosing timepoint (i.e., Day 2) are completed.

The SMC will perform overall ongoing review of safety data during the study. Study enrollment and administration of study treatments may be temporarily paused by the SMC for safety review if any of the following occur after study product administration and during the study's follow-up period:

- One or more serious adverse event(s) [SAE(s)]

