#### 3.3 Pharmacodynamics Endpoints

**Primary PK Endpoints:** The following PK parameters will be estimated after a single dose of COVID-HIGIV infusion:

- $AUC_{0-\text{last}}$ : area under the concentration-time curve from time 0 to the last quantifiable concentration after a single dose. Time 0 is defined as the end of infusion; time  $t$  is defined as time of the last quantifiable concentration.
- $AUC_{0-\text{inf}}$ :  $AUC_{0-\text{last}}$  plus the additional area extrapolated to infinity.
- $AUC_{0-14d}$ : AUC from time 0 to 14 days post-dosing.
- $AUC_{0-28d}$ : AUC from time 0 to 28 days post-dosing.
- $C_{\text{max}}$ : maximum observed post-dosing concentration.
- $T_{\text{max}}$ : time at which  $C_{\text{max}}$  occurs.
- $C_{\text{min28d}}$ : observed or estimated concentration (by interpolation/extrapolation) at 28 days post-dosing.
- $\lambda_z$ : terminal elimination rate constant after a single dose.
- $T_{1/2}$ : apparent terminal elimination half-life after a single dose.
- $CL$ : systemic clearance after a single dose.
- $V_z$ : volume of distribution after a single dose.

**Secondary PK Endpoints:** following body weight normalized PK parameters will be estimated as PK parameter divided by subject body weight (kg) at baseline.

- $C_{\text{max}}\text{BWN}$ : Body weight normalized  $C_{\text{max}}$
- $C_{\text{min28d}}\text{BWN}$ : Body weight normalized  $C_{\text{min28d}}$

[COVID-HIGIV]  
[EBS-CVH-003]

- $AUC_{0-14d}BWN$ : Body weight normalized  $AUC_{0-14d}$
- $AUC_{0-28d}BWN$ : Body weight normalized  $AUC_{0-28d}$
- $AUC_{0-last}BWN$ : Body weight normalized  $AUC_{0-last}$
- $AUC_{0-inf}BWN$ : Body weight normalized  $AUC_{0-inf}$

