### 8.5.6 Pharmacokinetic Analysis

All PK summary analyses will be conducted based on the PKS. Listings of PK concentration will be presented based on the COVID-HIGIV treated subjects with a flag indicating data points excluded from the PK analyses. Listings of PK parameters will be based on COVID-HIGIV treated subjects, with an indicator for parameter(s) considered as unreliable and being excluded from the summary analysis. A listing for the excluded subjects will be provided with reasons for exclusion.

PK concentration data will be summarized by nominal time points. The summary statistics for concentration data include n, arithmetic mean (Mean), standard deviation (SD), median, minimum (Min), maximum (Max), geometric means (Geo. Mean), and geometric percentage coefficient of variation (Geo. CV%).

PK parameters in [Table 2](#) will also be summarized with the descriptive statistics list above. Summary of  $T_{max}$  will include n, median, minimum, and maximum only. The Geo. CV% is calculated as,

$$\text{Geo. CV\%}(x) = 100 * (\sqrt{\exp(\text{variance of log}(x))} - 1), x = \text{PK concentrations}$$

Scatterplots for individual PK concentration-time profiles will be presented.

To investigate the dose proportionality of body weight normalized  $AUC_{0-14d}$  and  $C_{max}$  (if data permit), the power model will be used which fits a linear regression model with the log PK parameter against the log dose (COVID-HIGIV dose in mg/kg unit), i.e.,

$$\log(\text{PK parameter}) = \text{intercept} + \text{slope} * \log(\text{COVID-HIGIV dose})$$

Estimates of the intercepts and slopes along with 90% CIs will be reported. If the assumption of linearity is considered acceptable (i.e., adjusted  $r^2 > 0.8$ ) and if the 90% CI for the slope is entirely with (0.9, 1.1), the relationship between dose and the PK parameter will be concluded to be dose proportional for the dose range studied.

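### The dose-proportionality model divides exposure by weight when the dose is already per kg and has no weight term, so the slope's 90% CI can be wider than it need be

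*SAP*

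**What the plan says.** SAP 8.5.6 describes a power model used, if the data permit, "To investigate the dose proportionality of body weight normalized" AUC0-14d and Cmax. The log parameter is regressed on log dose ("COVID-HIGIV dose in mg/kg unit"), with an intercept and a slope and nothing else. Two conditions lead to a conclusion of proportionality. One begins "If the assumption of linearity is considered acceptable" and is defined as adjusted r² above 0.8. The other is "if the 90% CI for the slope is entirely with (0.9, 1.1".

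SAP 3.3 defines the normalisation: "following body weight normalized PK parameters will be estimated as PK parameter divided by subject body weight (kg) at baseline". I read it as applying to both parameters in the model, since the protocol (2.3.1) lists "CmaxBWN: Body weight normalized Cmax" among the secondary PK endpoints.

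The dose is weight-based before any analysis. The note to the arm table in SAP 2.2 says "COVID-HIGIV Dosage 1-3 are prepared by IP volume (mL) based on subject body weight (kg", with volume caps of 100, 200 and 400 mL that take effect at 100 kg. The same note says "the dosages in study arm label are in the unit of mg/kg". SAP 8.5.6 does not say whether its regressor is that label or the mg/kg received; SAP 9.1 summarises exposure in mg/kg. SAP 6.6 plans no covariate adjustment, on the ground that no formal hypothesis is tested.

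**The concern.** With mg/kg dosing, weight is already in the dose. Dividing the exposure by weight as well puts response and regressor on different footings, and the SAP gives no reason for doing so. If heavier subjects have larger clearance or volume, the division creates a weight trend in the response. With no weight term, that trend is counted as residual noise.

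The stakes are limited. Dose proportionality is neither an objective nor an endpoint, and the primary PK summaries do not depend on this model. It matters because this model carries a stated conclusion rule, the rule is decided by the width and position of a 90% CI from 24 subjects, and the protocol (1.3) says the PK parameters will inform dose selection.

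**Working it through.** The plan gives no precision or power figure for the slope, so there is none to reproduce.

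**Inputs from the documents.** Eight subjects at each of 100, 200 and 400 mg/kg (24 in the fit); a 90% CI; window (0.9, 1.1); dose cap at 100 kg.

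**Assumed, because the documents are silent.** PK CV 10 to 20%; weight CV 20% (15% as a check), log-normal with mean 78 kg and clipped to 45–115 kg; true slope 1; clearance or volume proportional to W^b with b from 0 to 1; all 24 evaluable.

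**Algebra.** Let D be the dose received in mg/kg. The dose in mg is D·W.
- Raw exposure ∝ D·W / W^b = D·W^(1−b).
- Normalised exposure ∝ D·W^(−b).

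With s the PK residual SD and sw the SD of log weight, the residual variance is:
- planned model: s² + b²·sw²
- un-normalised response, no covariate: s² + (1−b)²·sw²
- either response plus log weight: s²

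The planned fit is efficient only near b = 0 and the un-normalised fit only near b = 1.

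**Half-width.** Sxx = 16·(ln 2)² = 7.687, √Sxx = 2.773 and t(0.95, 22) = 1.717. Half-width = 1.717/2.773 × residual SD = 0.619 × residual SD. A half-width of 0.10 or less therefore needs a residual SD of at most 0.161. With s = 0.10 and sw = 0.20:
- b = 1: 0.619 × √(0.01 + 0.04) = 0.138
- b = 0.5: 0.619 × √(0.01 + 0.01) = 0.088
- b = 0: 0.619 × 0.10 = 0.062

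**Simulation.** 20,000 trials per setting, with the cap applied and actual mg/kg as regressor. Clipping the weights makes the half-widths slightly smaller than the formula gives. A separate re-run agreed and supplied the un-normalised values at intermediate b. Weight CV 20%, PK CV 10%:

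| b | Planned half-width | Un-normalised, no covariate | With log weight | Rule met, planned | Rule met, log weight |
|---|---|---|---|---|---|
| 1 | 0.133 | 0.061 | 0.063 | 0.3% | 67–68% |
| 0.75 | 0.108 | 0.068 | 0.063 | 3.6% | 67–68% |
| 0.5 | 0.085 | 0.085 | 0.063 | 24.1% | 67–68% |
| 0.25 | 0.068 | 0.108 | 0.063 | 56.3% | 67–68% |
| 0 | 0.061 | 0.133 | 0.063 | 70.3% | 67.1% |

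Other settings, with b in the same order (1 to 0):
- PK CV 15%: rule met in 0.1 / 0.6 / 3.9 / 11.5 / 16.1% as planned, about 14% with log weight.
- PK CV 20%: rule met in at most 1.3% under any model. Half-width 0.169 / 0.150 / 0.135 / 0.125 / 0.121 as planned, about 0.124 with log weight.
- Weight CV 15%, PK CV 10%: rule met in 3.6 / 15.6 / 39.0% as planned at b = 1 / 0.75 / 0.5, against about 67%.

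The mean planned slope was 1.000 to 1.008 throughout. Using the labelled instead of the received mg/kg widens the planned half-width by 0.002 to 0.008 at PK CV 10%.

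**The r² condition.** A CI inside (0.9, 1.1) has half-width of at most 0.1 and an estimate at least 0.9 plus the half-width, so slope/half-width ≥ 0.9/0.1 + 1 = 10. Then t ≥ 10 × 1.717 = 17.17, r² ≥ 17.17²/(17.17² + 22) = 0.931, and adjusted r² ≥ 1 − 0.069 × 23/22, about 0.927. The 0.8 condition never decides the conclusion. The bound is also 0.927 with log weight in the model.

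**The case against.** The strongest reply is that the gain is conditional and its condition is unknown. The exponent b decides whether there is a gain at all, and it cannot be read from the documents. At b = 0 the planned model is the better one: the added term widens the CI by about 3% (0.061 to 0.063) and lowers the pass rate from 70.3% to 67.1%. At b = 0.25 and PK CV 20% there is nothing to gain. This stands, and it rules out calling the covariate an unconditional improvement. The case for it is the asymmetry: a loss of about 3% at worst, against a halving of the CI at b = 1 and PK CV 10%.

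A second reply is to drop the normalisation and add nothing. That works if b is near 1 but fails at b = 0 as badly as the planned model does at b = 1. Only the covariate avoids having to know b.

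Third, the pass rates are optimistic. Withdrawn subjects are not replaced (protocol 4.3.2) and the PK Set can exclude subjects (SAP 5.2). At PK CV 10% the weight-adjusted model meets the rule in about 57% of trials with 7 per arm and 44% with 6. With 8 per arm and a true slope of 0.95 it does so in about 36%. This also stands, so the table is a best case.

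Fourth, the analysis is descriptive and models predefined secondary endpoints. That limits the importance of the point but does not explain why weight is divided out twice.

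Finally, SAP 2.3.3 has the PK statistician working on PK results under dummy identifiers during the study, so a late change of model could look data-driven. That is a fair constraint on timing.

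**Conclusion.** The point holds in a limited form. The planned model leaves weight scatter in the residual unless b is near 0, and the CI that decides the rule can then be up to about twice as wide as necessary (0.133 against 0.063 at b = 1, weight CV 20%, PK CV 10%). All three of those values are assumptions.

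Three stronger readings do not follow:
- A reader might infer that the slope is biased. Under the assumptions above its mean stayed within 0.01 of the true value.
- A reader might infer that adding log weight makes the rule attainable. It improves the chance of meeting the rule only at PK CV of about 15% or less. Above that, the (0.9, 1.1) window with 24 subjects is the binding limit and the benefit is at most a narrower CI.
- A reader might infer that the primary PK results are affected. They are not.

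This is worth considering, not essential.

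**What to change.** In SAP 8.5.6, fit log(PK parameter) = intercept + slope × log(mg/kg actually received) + gamma × log(baseline weight) for AUC0-14d and Cmax, and apply the 90% CI rule to the dose slope. The dose slope and its CI are identical for the raw and the normalised response, because dividing by weight only shifts gamma by 1; the response can stay as defined. Naming actual mg/kg as the regressor also settles the ambiguity above 100 kg. Amend SAP 6.6 to record this one covariate. Keep the normalised secondary endpoints as descriptive summaries. If a weight term is added, the r² condition could be worded as a partial r² for dose, but this is a wording point only and changes no conclusion.

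Make the change before unblinded PK data are seen. If that is no longer possible, report the weight-adjusted fit as a sensitivity analysis beside the planned model.

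The cost is SAP wording, one degree of freedom (22 to 21), and a CI about 3% wider if b = 0. No new data are needed, since weight is collected at screening and exposure in mg/kg is summarised under SAP 9.1. The protocol does not describe this model, so it needs no amendment.

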## 8.6 Other Exploratory Analysis

There is no exploratory endpoint in this study.

# 9 SAFETY ANALYSIS

## 9.1 Extent of Exposure

Treatment exposure measured by COVID-HIGIV volume (mL), body weight normalized volume (mL/kg) and dose (mg/kg), potency (AU) and body weight normalized potency (AU/kg) will be summarized for all subjects treated with COVID-HIGIV by analysis group.

Subject listings of treatment exposure and drug administration will be provided.

[COVID-HIGIV]  
[EBS-CVH-003]

## 9.2 Adverse Events

AEs will be coded to system organ class (SOC) and preferred term (PT) according to the Medical Dictionary for Regulatory Activities (MedDRA).

AEs reported from the signing of the ICF until immediately before the first dose of IP on Day 1, will be in generally recorded as Medical History, unless it is study procedure associated, which may be considered as non-treatment-emergent AE. A treatment emergent adverse event (TEAE) is defined as an AE that was not present prior to administration of the first dose of study medication and any study procedures and present after the first dose or procedure, or if it represents the exacerbation of an event that was present prior to the first dose or procedure.

Only TEAEs will be included in the summaries described below and 'AE' will refer to TEAE, unless otherwise specified. For AE summaries, an AE occurs on the first dosing date but without onset time will be counted as treatment emergent. AEs with missing start dates, but with stop dates overlapping into the treatment period will also be counted as treatment emergent.

A subject data listing of all AEs (including treatment-emergent AEs (TEAEs) and non-TEAEs) sorted by analysis group, subject ID and AE start date/time will be provided.

### 9.2.1 Overall Summary of AEs

The following list of AEs summaries will be provided by SOC and PT in tabulate format. The events will be sorted in descending frequency of subjects in the "Total" column for SOC, then PT, unless otherwise specified.

- All AEs
- All AEs occur within 72 hours post-dosing (from the start of infusion to 72 hours post the end of infusion)
- All AEs by maximum severity
- AEs related to study treatment (COVID-HIGIV or placebo)
- AEs of Grade 3 and higher severity
- AEs of Grade 3 and higher severity and related to study treatment
- AEs by analysis group sorted by PT in descending frequency among all COVID-HIGIV treated subjects AE Severity

The Investigator is responsible for the assessment of the severity of an AE using the following criteria:

- Mild (Grade 1): awareness of a sign or symptom but subject can tolerate.
- Moderate (Grade 2): discomfort enough to cause interference with normal daily activity.
- Severe (Grade 3): resulting in an inability to do work or do usual daily activity.

[COVID-HIGIV]  
[EBS-CVH-003]

- Potentially Life-Threatening (Grade 4): emergency room visit or hospitalization.
- Death (Grade 5)

Subjects having the same AE more than once will be counted once for each PT and once within each SOC at the maximum severity. If the severity is missing for one or more of the occurrences, the maximum severity of the remaining occurrences will be used.

### **9.2.2 AEs Related to Study Treatment**

Relationship of AEs to the study treatment will be assessed by the PI or designee, and reviewed by the Sponsor, using terms and scales “Unrelated”, “Possibly related”, “Probably related”, and “Definitely related”. If the relationship between the AE and the study treatment is determined to be “Possibly” or “Probably” or “Definitely” related, the event will be considered as related to the study treatment.

## **9.3 Deaths, Other Serious Adverse Events and Significant Adverse Events**

### **9.3.1 Deaths**

Deaths is not expected in this study with healthy participants. A subject listing of deaths (if any) will be provided as appropriate, including the primary causes of death.

### **9.3.2 Serious Adverse Events (SAEs)**

An SAE is an AE that results in death, is life threatening, requires inpatient hospitalization or prolongation of existing hospitalization, results in persistent or significant disability/incapacity, or is a congenital anomaly or birth defect.

- All SAEs will be tabulated by SOC and PT.
- All SAEs related to study treatment will be summarized by SOC, PT, and severity.

A subject data listing of all SAEs will be provided.

### **9.3.3 TEAEs Leading to Study Treatment Discontinuation and/or Study Withdrawal**

AEs leading to discontinuation or infusion interruption will be summarized by study arm and listed by subject.

## **9.4 Clinical Laboratory Tests**

### **9.4.1 Safety Laboratory Tests**

Clinical safety laboratory assessment includes the following –

- Chemistry panel: sodium ( $\text{Na}^+$ ), potassium ( $\text{K}^+$ ), chloride ( $\text{Cl}^-$ ), bicarbonate ( $\text{HCO}_3^-$ ), blood urea nitrogen (BUN), creatinine, glucose, total and direct bilirubin, alanine

[COVID-HIGIV]  
[EBS-CVH-003]

aminotransferase (ALT), aspartate aminotransferase (AST), and lactate dehydrogenase (LDH),

- Hematology panel: complete blood count (CBC); i.e., red blood cells, white blood cells, platelets, hemoglobin, and hematocrit, with differential (neutrophils, eosinophils, basophils, monocytes and lymphocytes).
- Urinalysis: PH, specific gravity, urobilinogen, blood, bilirubin, color, glucose, ketone, leukocyte esterase, nitrite, protein.

Numeric laboratory results and change from baseline will be summarized by analysis group at scheduled visits only.

The abnormality of the laboratory results (Low, Normal, High) will be assessed according to normal ranges. The clinical significance of abnormality will be assessed by PI. Laboratory results will be graded with severity grade 1 to 4 (grade 1=mild, through grade 4=potentially life-threatening) according to the DAIDS Table for Grading the Severity of Adult and Pediatric Adverse Events ([Appendix II](#)).

Values not meeting criteria for toxicity of at least grade 1 will be considered as grade 0. If laboratory tests with toxicity criteria for both increased and decreased directions exist (e.g., Sodium), toxicity grades for each direction will be presented separately (e.g., Sodium Increased versus Sodium Decreased).

For selected laboratory parameters, shift of abnormality (Low, Normal, High) and toxicity grade from baseline to the maximum/minimum post-dosing results will be tabulated with counts and percentages by analysis group and timepoint.

The qualitative results of urinalyses will be summarized by analysis group at scheduled visits. Count and percentage of subjects of each result category will be presented.

All laboratory records will be provided in the subject data listings, with applicable toxicity grades or abnormal flags displayed. A separate listing will be provided for post-baseline laboratory results at Grade 1 or higher.

## 9.5 Vital signs, Physical Findings and Other Variables Related to Safety

### 9.5.1 Vital Signs

Vital signs include the following parameters: oral temperature, seated blood pressure, resting heart rate, pulse oximetry and respiratory rate. Vital sign results and change from baseline will be summarized by time point and study treatment.

Vital sign results will be assessed and assigned a severity grade 1 to 4 (see [Appendix III](#)). Grade 0 includes all values not meeting criteria for severity of at least Grade 1. If vital signs with toxicity criteria for both increased and decreased directions exist (e.g., Blood pressure), analyses for each direction will be presented separately (e.g., Hypertension versus Hypotension).

[COVID-HIGIV]  
[EBS-CVH-003]

Shift of abnormality (Normal, Abnormal) and severity grade from baseline to 30 minutes and 1 hour post-dosing (post the end of infusion) results will be summarized by treatment group.

All vital sign records will be provided in the subject data listings.

